17.2 Grading and Reporting Adverse Events

- **Grading and Relationship to Drug**

The descriptions and grading scales found in the CTEP Version 4 of the NCI Common Terminology Criteria for Adverse Events (CTCAE) will be utilized for AE reporting. CTEP Version 4 of the CTCAE is identified and located at:

http://ctep.cancer.gov/protocolDevelopment/electronic_applications/ctc.htm.

AEs not covered by specific terminology listed should be reported with common medical terminology, and documented according to the grading scales provided in the CTCAE Version 4.

The relationship of event to study drug will be documented by the Investigator as follows:

Unrelated: The event is clearly related to other factors such as the participant’s clinical state, other therapeutic interventions or concomitant drugs administered to the participant.

Unlikely: The event is doubtfully related to investigational agent(s). The event was most likely related to other factors such as the participant’s clinical state, other therapeutic interventions, or concomitant drugs.

Possible: The event follows a reasonable temporal sequence from the time of drug administration, but could have been produced by other factors such as the participant’s clinical state, other therapeutic interventions or concomitant drugs.

Probable: The event follows a reasonable temporal sequence from the time of drug administration, and follows a known response pattern to the study drug. The event cannot be reasonably explained by other factors such as the participant’s clinical state, therapeutic interventions or concomitant drugs.

PROTOCOL TITLE: Phase 2A Study Evaluating a Chemokine-Modulatory Regimen in Patients with Colorectal Cancer Metastatic to the Liver

Definite: The event follows a reasonable temporal sequence from the time of drug administration, follows a known response pattern to the study drug, cannot be reasonably explained by other factors such as the participant's condition, therapeutic interventions or concomitant drugs; AND occurs immediately following study drug administration, improves upon stopping the drug, or reappears on re-exposure.

- **Reporting Adverse Events:** Routine AEs occurring between the start date of intervention until 30 days after the last intervention, or until the event has resolved, the study participant is lost to follow-up, the start of a new treatment, or until the study investigator assesses the event(s) as stable or irreversible, will be reported. New information will be reported after it is received.

Table 2 Guidelines for Routine Adverse Event Reporting (Regardless of Expectedness)

Attribution	Grade 1	Grade 2	Grade 3	Grade 4
Unrelated			X	X
Unlikely			X	X
Possible	X	X	X	X
Probable	X	X	X	X
Definite	X	X	X	X

17.3 Serious Adverse Events

A serious adverse event (SAE) is any adverse event (experience) that in the opinion of either the investigator or sponsor results in **ANY** of the following:

- Death.
- A life-threatening adverse event (experience). Any AE that places a participant or participants, in the view of the Investigator or sponsor, at immediate risk of death from the reaction as it occurred. It does NOT include an AE that, had it occurred in a more severe form, might have caused death.
- Inpatient hospitalization or prolongation of existing hospitalization (for > 24 hours).
- A persistent or significant incapacity or substantial disruption of the ability to conduct normal life functions.
- A congenital anomaly or birth defect.
- Important Medical Event (IME) that, based upon medical judgment, may jeopardize the participant and may require medical or surgical intervention to prevent one of the outcomes listed above.

Reporting Serious Adverse Events

All new SAEs occurring from the date the participant signs the study consent until 30 days after the last intervention or a new treatment is started, whichever comes first, will be reported. The RPCI SAE Source Form is to be completed with all available information, including a brief narrative describing the SAE and any other relevant information.

PROTOCOL TITLE: Phase 2A Study Evaluating a Chemokine-Modulatory Regimen in Patients with Colorectal Cancer Metastatic to the Liver

SAEs occurring after the 30 day follow-up period that the investigator determines to be possibly, probably or definitely related to the study intervention should be reported.

SAEs identified as an Unanticipated Problem by the Investigator must be reported. Please refer to Section 17.5 for details on reporting Unanticipated Problems.

17.4 Follow-Up for Serious Adverse Events

All related SAEs should be followed to their resolution, until the study participant is lost to follow-up, the start of a new treatment, or until the study investigator assesses the event(s) as stable or irreversible. New information will be reported when it is received.

17.5 Unanticipated Problems

An Unanticipated Problem (UP) is any incident, experience, or outcome that meets all of the following criteria:

- Unexpected (in terms of nature, severity, or frequency) given:
 - The research procedures that are described in the study-related documents, including study deviations, as well as issues related to compromise of participant privacy or confidentiality of data.
 - The characteristics of the participant population being studied.
- Related or possibly related to participation in the research (possibly related means there is a reasonable possibility that the incident, experience, or outcome may have been caused by the procedures involved in the research).
- Suggests that the research places participants or others at a greater risk of harm (including physical, psychological, economic, or social harm) than was previously known or recognized and if in relation to an AE is also deemed **Serious** per **Section 17.3**.

Reporting Unanticipated Problems:

The Reportable New Information (RNI) Form will be submitted to the CRS Compliance Office within 1 business day of becoming aware of the Unanticipated Problem. After review, CRS Compliance will submit the RNI to the IRB.

When becoming aware of new information about an Unanticipated Problem, submit the updated information to CRS Compliance with an updated Reportable New Information Form. The site Investigator or designated research personnel will report all unanticipated problems, whether related or unrelated to the investigational agent(s) to the IRB in accordance with their local institutional guidelines.

PROTOCOL TITLE: Phase 2A Study Evaluating a Chemokine-Modulatory Regimen in Patients with Colorectal Cancer Metastatic to the Liver

17.6 FDA Reporting

When RPCI is the IND holder the following describes the FDA reporting requirements by timeline for AEs and new safety findings that meet the criteria outlined below:

Within 7 Calendar Days

Any adverse event that meets **ALL** the following criteria:

- Related or possibly related to the use of the study drug;
- Unexpected; and
- Fatal or life-threatening.

Within 15 Calendar Days

Any adverse event that meets **ALL** the following criteria:

- Related or possibly related to the use of the study drug;
- Unexpected; and
- Serious but not fatal or life-threatening;

Or, meets **ANY** of the following criteria:

- A previous adverse event that is not initially deemed reportable but is later found to fit the criteria for reporting (report within 15 days from when event was deemed reportable).
- Any findings from other studies, including epidemiological studies, pooled analysis of multiple studies, or other clinical studies conducted with the study drug that suggest a significant risk in humans exposed to the drug.
- Any findings from animal or in vitro testing that suggest a significant risk for human participants including reports of mutagenicity, teratogenicity, or carcinogenicity or reports of significant organ toxicity at or near the expected human exposure.
- Any clinically important increase in the rate of occurrence of a serious, related or possibly related adverse event over that listed in the protocol or investigator brochure.

Sponsors are also required to identify in IND safety reports, all previous reports concerning similar adverse events and to analyze the significance of the current event in the light of the previous reports.

Reporting Process

The principal investigator or designee will complete and submit a FDA Form 3500A MedWatch for any event that meets the above criteria. Forms will be submitted to the CRS Compliance Office via email to [contact].

18 DATA MANAGEMENT AND CONFIDENTIALITY

18.1 Data Collection

Full build studies are managed by RPCI CRS Data Management for analysis by RPCI Biostatisticians. All electronic case report form (eCRF) data are captured for these studies.

PROTOCOL TITLE: Phase 2A Study Evaluating a Chemokine-Modulatory Regimen in Patients with Colorectal Cancer Metastatic to the Liver

Data management activities are performed using a CTMS system that enables the collection, cleaning and viewing of clinical trial data. CRS data management designs the study-specific database and facilitates development by the Information Technology team. Once the database design is approved by the Investigator, Statistician, and Clinical Research Coordinator, the database is put into production and data entry can begin. Data can be entered and changed only by those with the rights to do so into the eCRFs.

18.2 Maintenance of Study Documents

Essential documents will be retained per RPCI's policy for 6 years from the study termination date. These documents could be retained for a longer period, however, if required by the applicable local regulatory requirements or by an agreement with RPCI.

18.3 Revisions to the Protocol

RPCI may make such changes to the protocol as it deems necessary for safety reasons or as may be required by the U.S. FDA or other regulatory agencies. Revisions will be submitted to the IRB/ERC for written approval before implementation.

18.4 Termination of the Study

It is agreed that, for reasonable cause, either the RPCI Investigators or the Sponsor, may terminate this study, provided a written notice is submitted within the time period provided for in the Clinical Trial Agreement. In addition, RPCI may terminate the study at any time upon immediate notice if it believes termination is necessary for the safety of participants enrolled in the study.

18.5 Confidentiality

Any data, specimens, forms, reports, video recordings, and other records that leave the site will be identified only by a participant identification number (Participant ID, PID) to maintain confidentiality. All records will be kept in a limited access environment. All computer entry and networking programs will be done using PIDs only. Information will not be released without written authorization of the participant.

19 STATISTICAL PLAN

19.1 Study Design/Endpoints

This is a Phase 2A study of the chemokine-modulating regimen Celecoxib, IFN α , and rintatolimod. The regimen will be evaluated via serial biopsies comparing the quantity of tumor infiltrating CD8+ cells prior to therapy with that seen post-therapy. Tumor imaging will be repeated at day 46 (+/- 3 days) to assess objective response to therapy. Tumor infiltrating CD8+ cells in the biopsied tumor will be measured by quantitative RT-PCR and results will be expressed as a ratio to a housekeeping gene.

19.2 Power and Sample Size

Sample Size Determination: We consider a five-fold increase in TIL expression as clinically meaningful. In a series of 55 *ex-vivo* CRC tumor specimens from patients treated surgically for recurrent CRC, the log (base 10) transform of the TIL expression yielded an estimated mean = 1.2

PROTOCOL TITLE: Phase 2A Study Evaluating a Chemokine-Modulatory Regimen in Patients with Colorectal Cancer Metastatic to the Liver

and standard deviation = 0.9. A fivefold increase due to chemokine modulation would increase the mean from 1.2 to 1.9 (a 0.77 SD shift).

The sample size calculations are based on the primary analysis, where the change in TILs is evaluated using a one-sided permutation t-test. With a sample size of n=12 *evaluable patients*, the study design has 90% power to detect a 0.77 standard deviation increase (pre- to post-treatment) at a significance level of 0.1. Therefore we have an adequate design to detect a clinically meaningful increase in TIL expression.

Analysis Cohorts and Patient Replacement: Patients missing pre-treatment and/or post-treatment TILs are considered unevaluable for the primary endpoint, and will be replaced. Patients that receive at least one study dose will be included in the *safety analysis cohort*. Patients that are considered ‘evaluable’ for the primary endpoint will be included in the *primary analysis cohort*. All patients that receive at least one study dose and are followed for clinical outcomes will be included in the *secondary analysis cohort*.

Demographics: Patient characteristics will be summarized for each analysis cohort using the appropriate descriptive statistics – mean, standard deviation, and percentiles for continuous variables; and frequencies and relative frequencies for categorical variables.

19.3 Proposed Data Analysis

Primary Analysis: The *primary objective* is to determine the impact of a chemokine-modulatory regimen on the immune microenvironment of colorectal liver metastases. The *primary endpoint* is the change in TILs, as measured by CD8= transcript, which is treated as a continuous variable.

The TILs will be summarized by time-point (pre-/post-treatment) using the mean, median, standard deviation; and graphically using dot-plots. A 90% confidence interval for the mean change in TILs will be obtained using standard methods. Using a one-sided permutation paired t-test, the following hypotheses about the change in TILs will be evaluated:

$$H_0: \mu_d \leq 0 \text{ versus } H_A: \mu_d > 0,$$

where μ_d is the true change in TILs (post-treatment – pre-treatment).

This analysis will be limited to subjects who are considered evaluable for efficacy. Therefore the recommended sample size for efficacy is 12 *evaluable subjects*.

Secondary Analysis: The secondary objectives are to evaluate the clinical outcome of objective response and safety of the proposed therapy. The responses (based on RECIST v1.1 criteria) will be treated as binary data and summarized using frequencies and relative frequencies; with the objective response rate (ORR) estimated using a 90% confidence interval obtained using Jeffrey’s prior method. The safety analysis is described in Section 9.4.

Exploratory Analyses: The exploratory objectives are to evaluate the clinical outcomes of overall survival (OS) and progression-free survival (PFS). The OS and PFS will be treated as bivariate time-to-event data and will be summarized using standard Kaplan-Meier methods. OS will be defined as the time from the start of treatment until death due to any cause or last follow-up. PFS will be defined as the time from the start of treatment until disease progression (defined by RECIST 1.1) or last-follow-up.

PROTOCOL TITLE: Phase 2A Study Evaluating a Chemokine-Modulatory Regimen in Patients with Colorectal Cancer Metastatic to the Liver

Interim Analysis: As part of amendment #8, an interim analysis will be utilized to examine whether refinement of patient selection (i.e. earlier line) and tumor selection (i.e. selection of lesion and number of tumor cores) will improve: 1) the intra-subject variability observed in the first patients (likely due to choice of lesion and abundance of necrotic tissue), and efficacy with respect to the primary end-point (change in TILs).

The intra-class correlation coefficient (ICC) as an interim evaluation of the intra-subject variability associated with TILs. The conditional power for the one-sided paired t-test about the change in TILs will be calculated as an interim evaluation of efficacy.

The research team will meet to discuss these results and determine whether to: 1) continue enrollment in this patient cohort at the given dose level; or 2) incorporate a dose escalation scheme. If there is reduced intra-patient variability and potential evidence of efficacy (i.e. high ICC and conditional power), then the study enrollment will be completed as currently described. Otherwise, we may consider increasing the dose of Rintatolimod using an accelerated titration design (detailed in a subsequent amendment).

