7 STUDY TIMELINES

15 participants from RPCI will be enrolled to the study over approximately 48 months. Patients will be followed for PFS and survival for at least an additional 12 months.

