8.3 Exploratory Endpoints

- Median progression free survival by RECIST v1.1
- Median overall survival

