9.3 Follow-up Phase

Patients will be seen for an end of treatment visit to review adverse events, clinical outcome of therapy. If stable disease/response is demonstrated during repeat CT imaging, patients will continue in follow-up with CT imaging every 8 weeks until progression, clinical deterioration or withdrawal from the study. If in the clinical judgement of the treating team, it is in the best interest of the patient to pursue another therapeutic option, the patient will come off study and CT imaging will be obtained only as per SOC/protocol. 12 months of survival follow-up will be pursued by chart audit or if necessary phone contact. If the patient comes off study during the follow-up period to start a new treatment, the new treatment information will be captured in the database.

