2. At each time point, Physical exam to include assessment of Head/Ears/Eyes/Nose/Throat (HEENT), Skin, Chest/Lungs, Heart, Neck/lymph nodes, Abdomen including liver/spleen, Extremities and weight. Height to be collected at screening only. Physical exam does not need to be repeated on Day 1 if performed within 3 days prior to Day 1.

3. CBC with auto differential.

4. Glucose, BUN, creatinine, sodium, potassium, chloride, CO₂, calcium, total protein, albumin, alkaline phosphatase, AST, ALT, total bilirubin, amylase, lipase.

5. Within 7 days of Day 1 and as clinically indicated once on treatment in women of child-bearing potential only.

6. Blood (60cc) for in vitro assays will be drawn as outlined in section 11.2.

6^a. Day 3 only within 1 hour after end of infusion

7. Within 28 days prior to Day 1.

8. Vital Signs (blood pressure, pulse, respiratory rate and temperature) will be obtained at screening and end of treatment visits. On dosing days, vital signs will be obtained pre-treatment, 30 and 60 minutes post Rintatolimod (± 5 minutes).

9. Patients will be followed for survival status for 12 months after end of treatment visit. Phone contact/chart review is acceptable.

10. Restaging imaging CT/MRI to be performed on day 46 ± 3 days. If this scan demonstrates stable disease/response, patients will continue in follow-up with CT imaging every 8 weeks until progression, clinical deterioration or withdrawal from study. If in the clinical judgement of the treating team, it is in the best interest of the patient to pursue another therapeutic option, the patient will come off study and CT imaging will be obtained only as SOC/protocol.

11. Once every 3 months for up to 12 months after EOT visit to ascertain survival – both chart review and/or phone contact are acceptable

PROTOCOL TITLE: Phase 2A Study Evaluating a Chemokine-Modulatory Regimen in Patients with Colorectal Cancer Metastatic to the Liver

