¹ Non-CR/non-PD is preferred over SD for non-target disease since SD is used as endpoint for assessment of efficacy in trials so to assign this category when no lesions can be measured is not advised.

The best overall response is the best response recorded from the start of study treatment until disease progression, taking into account any requirement for confirmation. In general, the

Date 102920

PROTOCOL TITLE: Phase 2A Study Evaluating a Chemokine-Modulatory Regimen in Patients with Colorectal Cancer Metastatic to the Liver

participant's best response assignment will depend on the achievement of both measurement and confirmation criteria and will be determined by combining the participant's status of target lesions, non-target lesions, and new lesions.

- **Symptomatic Deterioration:** Participants with global deterioration of health status requiring discontinuation of treatment without objective evidence of disease progression at that time, and not related to study treatment or other medical conditions should be reported as progressive disease due to "symptomatic deterioration." Every effort should be made to document objective progression even after discontinuation of treatment due to symptomatic deterioration. Symptomatic deterioration that may lead to discontinuation of treatment include, but is not limited to, symptoms such as:
 - Weight loss > 10% of body weight.
 - Worsening of disease-related symptoms (e.g., worsening dyspnea, increasing pain/increasing requirement for narcotic analgesics).
 - Decline in performance status of > 1 level on ECOG scale.

Confirmation Measurement

If Day 46 CT scan demonstrates stable disease/response, patients will continue in follow-up with CT imaging every 8 weeks until progression, clinical deterioration or withdrawal from study.

Guidelines for Evaluation of Measurable Disease

All measurements should be taken and recorded in metric notation. All baseline evaluations should be performed as closely as possible to the beginning of treatment and never more than 4 weeks before the beginning of the treatment.

The same method of assessment and the same technique should be used to characterize each identified and reported lesion at baseline and during follow-up. Imaging-based evaluation is preferred to evaluation by clinical examination unless the lesion(s) being followed cannot be imaged but are assessable by clinical exam.

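### As written, Section 19.3 leaves death out of the PFS event, so the endpoint is time to progression and usually looks longer than PFS

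*Combined protocol and SAP*

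**What the plan says.** Section 19.3 (Exploratory Analyses) defines the two time-to-event endpoints in consecutive sentences and summarizes both by Kaplan-Meier.

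- Overall survival: "OS will be defined as the time from the start of treatment until death due to any cause or last follow-up".
- PFS: "PFS will be defined as the time from the start of treatment until disease progression (defined by RECIST 1.1) or last-follow-up".

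The other places that bear on PFS do not add death as an event:

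- Section 8.3 lists only "Median progression free survival by RECIST v1.1".
- Section 7: "Patients will be followed for PFS and survival for at least an additional 12 months".
- Section 9.3, for patients with stable disease or response: "patients will continue in follow-up with CT imaging every 8 weeks until progression, clinical deterioration or withdrawal from the study". Separately, "12 months of survival follow-up will be pursued by chart audit or if necessary phone contact".
- Appendix F, footnote 10: "Restaging imaging CT/MRI to be performed on day 46 ± 3 days".
- Appendix G tells the site to report as progressive disease "Participants with global deterioration of health status requiring discontinuation of treatment without objective evidence of disease progression at that time", provided the decline is not due to study treatment or another condition. It does not mention death.

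Sections 9.2 and 9.3 let a patient come off study for another treatment. Section 9.2 then asks for the next staging study, and Section 9.3 has the new treatment recorded in the database.

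**The concern.** The two definitions share one structure, an event or else last follow-up. In the PFS sentence the event is progression alone. A programmer who follows it would give a patient who died without a progression scan a censored time.

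The case can arise. Imaging may stop at clinical deterioration while survival contact continues, and a death before Day 46 comes before the first restaging scan. Eligible patients have unresectable metastatic disease and an ECOG status up to 2 (Section 3.1).

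The censoring date is also unclear. Section 7 follows patients for PFS and survival together, whereas Section 9.3 separates imaging from chart or phone contact. Last follow-up could therefore mean the last scan or the last contact.

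At stake is an estimate labeled median PFS that is not PFS and is usually too favorable. With about 15 patients, a few deaths can move the median. The primary CD8 endpoint, its power calculation and the interim evaluation do not use PFS.

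**Working it through.** **Inputs from the documents.** About 15 patients (Section 4). Restaging on Day 46 ± 3 days, then every 8 weeks (Section 9.3, Appendix F). End-of-treatment visit on Day 29 and 12 months of survival follow-up, so a nominal cut-off of 29 + 365 = Day 394. The plan states no PFS median, event count or power, so there is no figure to reproduce.

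**Assumptions.** The share of first events that are deaths without documented progression is not given; 10%, 20% and 30% are used. True medians of 60, 90 and 120 days are also assumed, with exponential event times.

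**Step 1: direction if deaths are censored at the death date.** The Kaplan-Meier estimate multiplies factors (1 − d/n), with d events among n at risk. Censoring a death at its own date leaves every risk set unchanged and only reduces d. Each factor is equal or larger, so the curve is unchanged or higher.

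**Step 2: direction if deaths are censored at the last scan.** The patient now leaves the risk set before death. A progression recorded in between is divided by a smaller n, so the curve can drop further. Two hypothetical trials of 15 show this.

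*Off-schedule scan.* Seven progress on Day 46; two are stable on a Day 43 scan and die on Days 80 and 90; six stay event-free.

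| Handling of the two deaths | Survival estimate | Median |
|---|---|---|
| Event | S(46) = 8/15 = 0.533; S(80) = 7/15 = 0.467 | Day 80 |
| Censored at death | stays at 8/15 | not reached |
| Censored at Day 43 scan | S(46) = 6/13 = 0.462 | Day 46 |

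*Leaving scheduled scanning.* Four progress on Day 46 and three on Day 102. Eight are stable on Day 46, leave for other therapy and die on Day 300.

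| Handling of the eight deaths | Survival estimate | Median |
|---|---|---|
| Event | S(46) = 11/15; S(102) = 8/15; S(300) = 0 | Day 300 |
| Censored at death | stays at 8/15 after Day 102 | not reached |
| Censored at Day 46 scan | S(46) = 11/15; three at risk on Day 102, all progress, so S(102) = 0 | Day 102 |

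**Step 3: illustrations of size.** These describe the model, not this trial.

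- *Continuous time, no scan grid.* If a share q of first events are deaths, the progression hazard is (1 − q) times the total, so the median is the true median divided by (1 − q). The ratios are 1/0.9 = 1.11, 1/0.8 = 1.25 and 1/0.7 = 1.43.
- *Large sample on the scan grid.* The median is unchanged in 6 of 9 scenarios. It is one 56-day interval later in the other three: true median 90 days with 20% or 30% deaths (158 v 102), and 120 days with 30% (214 v 158).
- *Simulation, n = 15.* There are 4,000 trials for each of 9 scenarios, with scans moved at random within ±3 days (stated for Day 46, assumed for later scans). The table gives the percentage of trials in which the median is more than 7 days longer than with death counted.

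| Assumed death share | Censored at death | Censored at last scan |
|---|---|---|
| 10% | 14–24% | 12–21% |
| 20% | 33–45% | 29–41% |
| 30% | 52–65% | 47–61% |

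The median is shorter in 0 of 36,000 trials under death-date censoring and in 147 of 36,000 (0.4%) under last-scan censoring. If 30% of patients are assumed to leave after each scan, the last-scan figure rises to about 3–5%.

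**The case against.** **Drafting slip.** The endpoint is called progression-free survival throughout, the plan never uses the word censored, and a statistician might count deaths by convention. That is plausible, and the documents cannot show how a death would be coded. What stands is that the plan's own explicit definition yields time to progression if followed.

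**Appendix G covers the gap.** This gives little mitigation. The rule applies to deterioration that requires stopping treatment, and the last planned dose is Day 17. Decline after that, including between Day 17 and the Day 46 scan, hardly meets the wording. The rule does not make death an event.

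**The size is a product of the model.** This stands. The death share, medians, event-time distribution and 7-day threshold are all choices. Without a scan grid, counting any lengthening, the percentages become 52%, 79% and 92% for shares of 10%, 20% and 30%.

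**Adding death alone is not enough.** This also stands. In the second example above, eight deaths long after the last scan, and after new therapy, move the median from Day 102 to Day 300. The definition needs a rule for such deaths.

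A reader might infer that the written definition always lengthens PFS. That holds for death-date censoring, but the documents do not settle the censoring date, and under last-scan censoring both examples reverse it.

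**Conclusion.** The omission is clear in the text. As written, a known death without documented progression would be censored, and the estimate is time to progression. The usual effect is a longer median. This is guaranteed not to reverse only under death-date censoring; under last-scan censoring it is a tendency. If no patient dies without documented progression, there is no effect.

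The size cannot be stated from the documents, and every percentage above rests on assumed values. Confidence is high on the omission and low on the size.

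Severity is minor. A reader might infer that the trial's main conclusion is inflated. The documents do not support that: PFS is exploratory, the trial has a single arm, and PFS has no target, comparator, test or decision rule.

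**What to change.** In Section 19.3:

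1. Define PFS as the time from start of treatment to the earlier of RECIST 1.1 progression or death from any cause. Censor patients without an event at the last adequate tumor assessment.
2. State one rule for scans and deaths after new anticancer therapy, and for deaths after missed scans. One option is to censor at the last adequate assessment before new therapy, with a sensitivity analysis that counts all deaths.
3. State whether symptomatic deterioration under Appendix G is a PFS event.

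The cost is wording only, with a cross-reference in Sections 9.2 and 11.1.6, where off-study scans are requested. Survival status and new-treatment information are already collected. The PFS estimate will usually be slightly less favorable.
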